4 STUDY DESIGN

- This is a prospective, multicenter cohort study of DH. For the study, practitioners and patients will be recruited from six National Dental PBRN regions across the US.
- The study population will consist of adult dental patients (19 years old or older) who have DH and the practitioners who provide treatment for DH. Dental practitioners are included in the population being studied because diagnostic modalities as well as treatment recommendations and approaches for DH are being studied. It is anticipated that approximately 180 dentist practitioners across the US will be enrolled (approximately 30 practitioners per National Dental PBRN region). Each dental practitioner will enroll approximately 14 study patients with an enrollment aim of 2,520 adult patients.
- The prospective, observational, multicenter design of the study will allow us to construct a picture of how patients with DH are cared for in dental offices across the US and how practitioner-, practice-, patient- and tooth- characteristics relate to the selected treatment(s) and approach(es) to care. The proposed study will provide further understanding about DH management based on a sample of US dental providers enrolled in the network and may provide data to establish guidelines for treating DH. The usual and customary treatment of DH that dentists apply in their practice will be assessed.
- After enrolling in the study and providing consent, practitioners will receive a link to a secure webpage and will be asked to complete an online questionnaire before recruiting and enrolling patients to the study.
- To determine if a patient meets the criteria for study inclusion, the patient must first indicate intraoral pain/sensitivity by self-report. Patients with a medical condition that could interfere with reliable pain reporting (e.g., cognitive impairment, dementia), chronic pain condition (fibromyalgia, lower back pain, irritable bowel syndrome, temporo-mandibular joint (TMJ) disorder), and patients who report having taken analgesics more than three times in the past week will be excluded from the study. Next, the practitioner will perform an oral examination to assess other causes of tooth sensitivity such as pulpitis or dental infection. A diagnosis of DH will be made when the practitioner has excluded other etiologies of odontogenic pain.

- Study patients will complete baseline assessments in dental offices and then will complete follow-up assessments 1-, 4- and 8-weeks post-baseline visit via an online or mailed questionnaire to record patient-reported pain outcomes. Patients who do not have a reduction of symptoms after the first-line treatment may return to the participating dentist due to continued discomfort and/or dentists' recommendation for a second-line treatment. If this occurs within 8 weeks of the initial treatment, study procedures (VAS, LM scales, and clinical exam) will be repeated for the second-line treatment administered or prescribed. The same process will apply if a third-line treatment is administered or prescribed. For patients who receive second- or third- line treatment, follow-up assessments will be obtained via online or mailed questionnaire at 1-, 4- and 8- weeks after the initiation of the second- or third-line of treatment, and follow-up assessments from the previously administered or prescribed treatment will no longer be warranted. Patients will be followed until approximately 8 weeks after the last administered treatment of DH, if it occurs within 8 weeks of the initial treatment. Patients' participation in the study will be 8 to 24 weeks as presented in the study flow diagram (page xi).
- It is anticipated that each practitioner will be able to enroll approximately 14 patients in 2-4 months. It is expected that the study will be fully-enrolled in approximately 6 months.
- The study duration for patients will be at minimum 8 weeks, to include in-office treatment for DH followed by follow-up assessments via online or mailed questionnaire at 1-, 4- and 8- weeks after treatment. Patients who return for second- or third-line treatments during the initial 8-week period due to pain and/or dentist's recommendation will be followed through 8 weeks after the last administered and/or prescribed treatment (maximum study length for patients is approximately 24 weeks).
- The Study Team will pilot test the practitioner online questionnaire with up approximately six practitioners to assess it in terms of length and acceptability. The Study Team will refine the questionnaire based on practitioner feedback and administer the revised questionnaire to 24 additional practitioners to quantify and document test-retest reliability. The website will be assessed for acceptability and Internet browser compatibility of the electronic questionnaire prior to administration with study participants.
- The same team (as above) of six practitioners enrolled in the study will be asked to pilot the data collection process, including online questionnaires and patient assessments, and modifications will be made as appropriate or necessary. During this phase, each practitioner will enroll approximately five patients in the study. These practitioners along with the 24 test-retest practitioners may continue to enroll patients (approximately 14 patients) unless there are changes to the critical data elements of the study as a result of the pilot. The pilot data will be included in the final analysis of the data unless certain data elements change as a result of the pilot.

5 STUDY ENROLLMENT AND WITHDRAWAL

5.1 Subject Inclusion Criteria

In order to be eligible to participate in this study, a practitioner must meet the following criteria:

- Any National Dental PBRN practitioner (i.e., general dentist and specialist) who is enrolled in the network at the full participation level.
- Practitioner affirms that the practice will devote sufficient time to allow for all of the study procedures.

The subject population for the study will be derived from the National Dental PBRN practices participating in the study. The expected sample for the study will include approximately 180 practitioners, each enrolling approximately 14 patients presenting with DH, for a total sample size of 2,520 patients.

In order to be eligible to participate in this study, a potential study patient must meet all of the following criteria:

- Agrees to participate in the study and complete the informed consent requirements according to the National Dental PBRN region approvals.
- Willing to comply with all study procedures and be available for the duration of the study.
- Age \geq 19 years.
- Reports having a sensitive tooth or teeth (3rd molars will be excluded) diagnosed with DH*.
- Has access to a phone, and agrees to receive text messages, emails, or phone calls related to the study. (The patient's preferred method of contact will be ascertained).
- Willing to be contacted on a regular basis by each of these entities: the practice, Regional Coordinator (RC), and the Westat Coordinating Center (CC).
- Willing to provide contact information of one person living at a different address who will know the patient's whereabouts in the event the patient cannot be reached.

* A diagnosis of DH will be based on the following from the patients' history and clinical examination: a) Patient's self-report of tooth pain, and b) Practitioner's exclusion of other dental and periodontal conditions that may be etiologies of tooth pain. Conditions

that need to be ruled out when diagnosing DH are listed in the exclusion criteria below. DH will be therefore a diagnosis of exclusion (Holland et al., 1997).

5.2 Subject Exclusion Criteria

A patient who meets any of the following criteria will be excluded from participation in this study:

- Has a medical condition that could interfere with reliable pain reporting (e.g., cognitive impairment, dementia).
- Has a chronic pain condition (fibromyalgia, lower back pain, irritable bowel syndrome, TMJ disorder).
- Has odontogenic pain (pain due to pulpitis, dental infection).
- Reports having taken analgesics (e.g., nonsteroidal anti-inflammatory drugs (NSAIDs), narcotics) more than three times in the past week.

5.3 Strategies for Recruitment and Retention

5.3.1 Practitioner Recruitment

We have estimated that we need to enroll approximately 180 practitioners to participate in this study; approximately 30 practitioners per National Dental PBRN region. This is based on the targeted enrollment of approximately 2,520 patients presenting with a sensitive tooth or teeth. All National Dental PBRN practitioners will be eligible to be approached for participation in this study. The practitioners will be asked for their interest in participating in the study. If more than 180 practitioners would like to participate in the study, practitioners will be selected systematically to provide a representative sample. The first priority will be to select practitioners on the basis of geographic region, with the aim of enrolling 30 practitioners per National Dental PBRN region. If there will be more than 180 practitioners and more than 30 practitioners from the National Dental PBRN region who would like to participate in the study, additional selection criteria will be used in the following significance: type of practice (solo practitioner, small group practice, large group practice, community dental practice), location (urban, suburban, rural), practitioner's experience (number of years in practice), practitioner's gender, race/ethnicity and age to obtain a representative cohort of practitioners. The RCs from the six regional administrative sites (RAS) will assist in recruitment of the practitioners to the study. RCs have a positive and close rapport with the network enrollees. Practitioners will be compensated for their time allocated to the study. Practitioners will receive \$50 for completing the online study questionnaire and \$25 for each patient office visit.

5.3.2 Patient Recruitment

We plan to enroll approximately 2,520 patients in an approximate 4-6-month period. Each practitioner will be asked to recruit approximately 14 patients. Recent data from

the Northwest PRECEDENT network have shown that the prevalence of DH among the patients seen by the practitioners enrolled in the previous network was 12.3% (Cunha-Cruz et al., 2013).

Any dental or hygiene visit will be eligible for patient recruitment to the study. A convenience sampling approach will be used to enroll patients in the study with an emphasis upon enrolling the first 14 patients presenting to the dental office who meet the eligibility criteria.

Patients presenting with DH at any dental visit in the dental office will be eligible for the study. Designated office personnel will introduce the study to patients who meet the inclusion criteria when they are seen for a dental appointment. Patients who meet eligibility criteria and show interest in participating in the study will be invited to participate, and a designated person will perform informed consent procedures. It is anticipated that in most instances it will be a dentist who will perform informed consent procedures. Patients will receive \$125 for their participation - \$25 upon completion of the baseline office visit, \$25 upon completion of the follow-up assessment at 1 week, \$25 upon completion of the follow-up assessment at 4 weeks and \$50 upon completion of the study.

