3.2.2 Secondary Outcomes

The proposed study will be conducted in six regions of the National Dental PBRN, allowing for a comparison among regions in relation to practitioners' approach(es) to care and treatment of DH based on the patient-, practitioner-, practice- and tooth- level characteristics. To explore the association between the above level characteristics and approach(es) to treatment for DH listed above, several patient-, practitioner-, practice- and tooth- level characteristics will be collected at baseline.

Patient characteristics:

Because this objective will explore characteristics that may contribute to practitioners' selected treatment(s) and approach(es) to care, the practitioner will be asked about the following patient variables at/or soon after the baseline visit:

Patient's predisposing variables: prior periodontal surgery and/or scaling and root planing, recent bleaching history, previous DH episodes and previous/current treatment modalities if any.

Patient's enabling variables: out-of-pocket cost for treatment and/or follow-up appointments after considering dental insurance coverage.

Practitioner characteristics:

The following practitioner variables will be collected upon enrolling in the National Dental PBRN by means of the enrollment questionnaire: age, gender, race/ethnicity, and year of graduation from dental school.

Knowledge about the etiology of DH and predisposing factors related to DH will be ascertained in the practitioner online questionnaire at study enrollment.

Practice characteristics:

The following practice variables will be collected from the practitioner as he/she enrolls in the National Dental PBRN by means of the enrollment questionnaire: practice size, location, practice business, wait time for new patients to be seen, number of patient visits per week, and hours of patient care per week.

Tooth (teeth) characteristics:

The following patient sensitive tooth (teeth) variables will be collected at the baseline visit: number of teeth that are sensitive, tooth (teeth) location, gingival recession, exposed dentin, recent periodontal surgery relating to the sensitive tooth (teeth), number of remaining teeth (surrogate for oral/dental functioning), whether or not the sensitive tooth has a restoration and, if so, the type of restoration, and location and number of surfaces restored.

Patient Satisfaction:

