6.6 Study Visits for Patients Returning for Additional Treatment

- Patients who do not have a reduction of symptoms after the first-line treatment may return to the participating dentist for a second-line treatment due to continued discomfort and/or dentist's recommendation if the dentist routinely utilizes a "stepped approach" to DH management. If this occurs within 8 weeks of the initial treatment, study procedures (VAS, pain intensity, clinical exam) will be repeated for each second-line and third-line treatment that is administered or prescribed.
- Recommended (by dentist) and actual (when appointment occurs) time interval(s) between treatment(s) will also be recorded. Patients will be contacted via text message system, phone or email 1-, 4- and 8-weeks post-additional treatment and will be followed until 8 weeks after the last administered DH treatment.

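### Objective 3 pools patients starting, stepping up and continuing a DH treatment, yet reads differences between modalities as treatment effects

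*Protocol*

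**What the plan says.** **Entry.** The inclusion criterion in Protocol Section 5.1 is a diagnosis: "Reports having a sensitive tooth or teeth (3rd molars will be excluded) diagnosed with DH". Section 5.3.2 adds "Any dental or hygiene visit will be eligible for patient recruitment to the study", and then "Patients presenting with DH at any dental visit in the dental office will be eligible for the study". Section 5.2 has four exclusions, and the only one that looks back at recent use concerns pain relief: "Reports having taken analgesics (e.g., nonsteroidal anti-inflammatory drugs (NSAIDs), narcotics) more than three times in the past week". None concerns past or present DH treatment.

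**Line numbering.** Section 6.6 treats the enrolment treatment as the first line: "Patients who do not have a reduction of symptoms after the first-line treatment may return to the participating dentist for a second-line treatment". Section 6.6.1 dates the second-line visit 1 to 56 days from the study baseline, and Section 6.6.2 dates the third from the second. Line is thus a count of study visits, not of steps within the patient's DH episode.

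**History.** Section 3.2.2 has the practitioner report, at or soon after baseline, "previous DH episodes and previous/current treatment modalities if any". The stated purpose is to explore what drives the choice of treatment. Section 3.2.1 says pain outcomes will be described by predisposing variables. Its examples are age, gender, race/ethnicity and education.

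**Analysis.** In Section 11.2, the Objective 3 model has random effects for practitioner and patient, and fixed effects for time and modality. The time-by-modality interaction is the test of main interest. The section grants that change within one group mixes treatment with natural course. It then says that comparisons between groups do reflect differences in treatment effect, because causes common to both groups drop out.

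**The concern.** Sections 2.1 and 2.2 say that some dentists treat DH in steps over several visits, so patients in mid-sequence at enrolment are foreseeable. Three kinds of patient can sit under one modality at Day 0: those receiving their first treatment, those moving on after an earlier treatment, and those continuing something they already use. The third kind may have no change in exposure at Day 0.

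If modalities tend to be used at different steps, the mix of these patients differs between them. A modality used mainly after failure is then judged in patients who have already not responded to something else. A home-use product may be judged partly in patients who were on it before the study. Neither is a cause common to all groups, so the cancellation argument in Section 11.2 does not cover them. At stake is the interaction test of primary interest and the reading given to it.

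**Working it through.** **1. Reproduce the plan's own figure.** Section 11.1 gives a detectable difference in VAS change of 0.095 SD (20 patients per dentist, ICC 0.0) to 0.160 SD (10 per dentist, ICC 0.05).

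Inputs from Section 11.1: 180 dentists, two equal groups, 5% type I error (taken as two-sided; the protocol does not say) and 80% power.

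- Effective N = 180 × m / (1 + (m − 1) × ICC), where m is patients per dentist.
- Detectable difference = (1.960 + 0.842) × √(2 / n), with n = effective N / 2 per group.
- m = 20, ICC 0: effective N = 3,600; difference = 0.0934 SD (stated 0.095).
- m = 10, ICC 0.05: effective N = 1,800 / 1.45 = 1,241; difference = 0.159 SD (stated 0.160).

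The stated figures reproduce closely. At the planned m = 14, the difference is 0.112 SD with ICC 0. With ICC 0.05, effective N = 2,520 / 1.65 = 1,527 and the difference is 0.143 SD.

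**2. Size of the possible bias.** To a first approximation, the bias in a comparison of two modalities is

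bias = (difference in share previously treated) × (effect of earlier treatment on VAS change, in SD).

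The protocol gives neither input, so all of these are assumptions:

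| Difference in share | Effect of earlier treatment | Bias |
|---|---|---|
| 10 points | 0.2 SD | 0.02 SD |
| 20 points | 0.5 SD | 0.10 SD |
| 30 points | 0.5 SD | 0.15 SD |
| 50 points | 0.5 SD | 0.25 SD |

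The lower rows reach or pass 0.143 SD; the first row is negligible. The two-group figure is the most favourable for power. With more and smaller modality groups the detectable difference grows, but the bias does not shrink with sample size.

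**3. Cost in precision of separating the patients.** Suppose a share f is set aside, so that m = 14 × (1 − f), with ICC 0.05:

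| f (assumed) | Patients | Effective N | Detectable difference |
|---|---|---|---|
| 0 | 2,520 | 1,527 | 0.143 SD |
| 10% | 2,268 | 1,435 | 0.148 SD |
| 25% | 1,890 | 1,281 | 0.157 SD |
| 50% | 1,260 | 969 | 0.180 SD |

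For f = 25%, m = 10.5 and effective N = 1,890 / 1.475 = 1,281. Power for the plan's medium effect of 0.5 SD stays at about 100% in every row. The issue is therefore confounding, not power.

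**The case against.** The case on the other side is substantial, and much of it stands.

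- **Open entry is deliberate.** The study sets out to describe how DH patients are cared for in practice. A washout or new-episode rule would work against that aim, and its absence is not a fault.
- **Objective 2 is not harmed as planned.** A reader might infer that the reported first-line treatment mix will be shifted toward treatments kept for failures. Section 11.2 plans no first-line percentage. It tabulates modalities used during the study, and a modality given after an earlier one is correctly counted as received.
- **Later treatment is not analysed as first-line.** A reader might infer this from the numbering, but the Objective 3 model has no line term. These patients are pooled, not misclassified within the model.
- **Stepped care is not measured by return visits alone.** A reader might infer that it will be under-counted. Section 3.2.1 also asks practitioners directly about a staged approach.
- **The history might yet be used.** The list of predisposing variables in Section 3.2.1 is open-ended, and Section 3.2.2 files treatment history under the same term. This softens the point. But the list does not name earlier treatment, and the model in Section 11.2 does not include it.
- **Such detail often belongs in the analysis plan, which is not at hand.** That is fair for the exact derivation of a variable. It does not cover the model terms and the interpretation that the protocol itself states.
- **No frequency is given.** This stands in full. How the case report form records advice to continue a product also cannot be seen.

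**Conclusion.** The point holds for Objective 3 only. As written, the model pools patients who are starting, stepping up or continuing, and the protocol's reason for reading modality differences as treatment effects does not extend to earlier failure or continuation. The first-line label, counted from study baseline, is consistent within the protocol. It should not be taken to mean the first treatment of the episode.

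The size cannot be derived from the documents. Under the assumptions shown, the bias is anywhere from trivial (0.02 SD) to larger than the study's own detectable difference (0.25 against 0.143 SD). The conclusion rests on the share of previously treated patients differing by modality. That is plausible where care is stepped, but the protocol does not demonstrate it. This is an improvement worth making before the pain analysis is fixed; it does not invalidate the design.

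**What to change.** 1. Keep entry open. In Sections 4 and 6.6, call the enrolment treatment the 'first study treatment', or state that line is counted from study baseline.
2. Use the history described in Section 3.2.2 to class each enrolment treatment as a first treatment, a further treatment after an earlier one, or continuation of a current modality. First confirm that the history form can separate these three; the protocol does not say whether treatment dates are recorded.
3. In Objective 3, add this class and its interaction with time to the model, or report trajectories by class. Include one comparison of modalities that leaves out continuers.
4. Qualify the sentence in Section 11.2 on treatment effects: shared causes cancel only where they are equally present across modalities, and modality was chosen by the dentist.

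The cost is one derived variable, some wording, smaller subsets and somewhat wider intervals. If 25% of patients were set aside (an assumption), the detectable difference at ICC 0.05 would move from about 0.143 to 0.157 SD. Extra data collection is needed only if the history form cannot make the distinction.

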5.3.3 Patient Retention

Patient retention is important to this study and follow-up data will be collected independently of in-office visits. The subject retention plan is presented in Appendix B. Study patients will be asked to complete follow-up assessments on a designated webpage 1-, 4-, and 8- weeks after the baseline visit. According to the US census data, it is estimated that about 70% of US households have computers with Internet access. Patients who do not have access to the computer with Internet will return the study documents by mailing them to the designated RC 1-, 4- and 8- weeks post-baseline. A designated office person will provide study documents with instructions to patients who would like to return study data collection forms via US mail. Patients who return for second- or third-line treatments during the initial 8-week period will be followed for an additional 8 weeks after the last administered/prescribed treatment in the same manner.

Based on patients' preferences, study patients will be contacted via a text message system or phone message to their designated phone number or will receive an email prior to each follow-up interval (1-, 4-, and 8- weeks after the baseline visit) and will be asked to complete the appropriate assessment. Two to three contact attempts per assessment will be implemented.

The RCs, with the assistance from the CC, will follow up with patients who do not complete the web-based or mail surveys by the due date to encourage them to complete study procedures.

